Next visit will be performed after at least 24 sachets have been taken (i.e. 4 or 5 days after the first visit (i.e. Day 5 or Day 6)).

Under no circumstances will subjects be enrolled more than once. Each investigator will also maintain a record of all subjects enrolled into the study (i.e. who signed the informed consent form). Records up to the time of premature termination should be completed. In the event that the subject was not receiving IMP, the primary reason will be recorded.

5.2.2 *Visit 2 (follow-up or End of study, Day 5 or Day 6)*

The following procedures will be performed:

- Adverse events will be reported by subject since the last visit and will be collected.
- The Investigator will check in the DEB if clinical data were appropriately recorded and if the study drug was appropriately used.
- Any change in the concomitant medication and/or surgical procedures since Visit 1 will be checked and recorded in the eCRF.
- A physical examination and body weight measurement will be performed.
- Vital signs (blood pressure, heart rate in sitting position, respiratory rate, body temperature and body weight) will be checked.
- Faecal microbiological results will be recorded
- Visit Status will be recorded

In case of recovery, the study treatment will be stopped. A last visit (Visit 3) will be planned at Day 9 or 10 for subjects who did not recover by Visit 2

5.2.3 *Visit 3 (End of study if patient is not recovered at Visit 2, Day 9 or Day 10)*

- Adverse events will be reported by subjects since the last visit and will be collected until 7 days after the last treatment intake.
- Any change in the concomitant medication and/or surgical procedures since Visit 2 will be checked and recorded in the DEB.
- A physical examination and body weight measurement will be performed.
- Vital signs (blood pressure, heart rate in sitting position, respiratory rate body temperature and body weight) will be checked.
- The Investigator will check in the DEB if clinical data were appropriately recorded and if the study drug was appropriately used. A copy of the DEB will be kept in the subject's file and the original will be sent to the Sponsor (Data Management).
- Visit Status will be recorded

Treatments units with used and unused sachets will be kept by the investigator.

5.2.4 *Early Withdrawal Visit*

- Adverse events will be reported by subjects since the last visit and will be collected until 7 days after the last treatment intake.

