10.2 Sample Size Determination

Assuming a median time to recovery of 55 hours in the active group and 70 hours in the placebo group (corresponding to a difference of 15 hours as evidenced in the Khediri et al study [7], 363 evaluable subjects per treatment group (726 in total) will be required in order to detect such a difference using a two-sided Gehan- Wilcoxon test at a significance level of 5% and a power of 80%.

It is assumed a maximum of 5% subjects prematurely withdrawn without recovery and a maximum of 10% nonevaluable subjects (because of poor/incomplete diary (DEB) completion).

Accordingly, 854 subjects (427 per treatment group) have to be randomized in order to achieve an 80% power

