1.1.2 Secondary objectives

The secondary objectives of the study are as follows:

- To demonstrate that diosmectite efficacy is superior to placebo regarding other efficacy criteria.
- To assess the clinical tolerance of diosmectite versus placebo

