1.3.4 Planned sample size

Assuming a median time to recovery of 55 hours in the active group and 70 hours in the placebo group (corresponding to a difference of 15 hours as evidenced in the Khediri et al study [1]), 363 evaluable subjects per treatment group (726 in total) will be required in order to detect such a difference using a two-sided Gehan-Wilcoxon test at a significance level of 5% and a power of 80%.

It is assumed a maximum of 5% of subjects prematurely withdrawn without recovery and a maximum of 10% of non-evaluable subjects (because of poor/incomplete diary completion). Accordingly, 854 subjects (427 per treatment group) will be required in order to achieve an 80% power.

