3.2.2.1 Adverse events

Adverse events will be coded using the Medical Dictionary for Regulatory Activities (MedDRA) Version 22.0.

Listings will be presented and sorted by treatment group, subject id, start time of AEs, primary system organ class, preferred term and verbatim text for all adverse events recorded during the study.

Listings of serious adverse events (SAE), adverse events leading to withdrawal and listings of deaths will also be presented.

Adverse events will be monitored from the time that the subject gives informed consent and throughout the study until 7 days after the end of study treatment. A TEAE is defined as any AE that occurs during the active phase of the study (i.e. from the first study drug intake until 48h after last study drug intake) and if:

- it was not present prior to receiving the first dose of IMP, or
- it was present prior to receiving the first dose of IMP but the intensity increased during the active phase of the study, or
- it was present prior to receiving the first dose of IMP, the intensity is the same but the drug relationship became related during the active phase of the study.

Treatment Emergent Adverse Events (TEAE) will be flagged (*) in the adverse events listing and will be summarised.

Related adverse events are those events with causality missing or related.

An overall summary table of all AEs with the number and percentage of subjects with at least one:

- AE,
- TEAE,
- TEAE by intensity,
- TEAE by causality,
- TEAE by intensity and causality,
- SAE,
- TEAE leading to premature withdrawal of study.

Note: In the event of multiple adverse events (corresponding to different PTs) being reported by the same subject, each subject is counted for each intensity level, each causality level or each intensity and causality combined level. That means that the total of subjects for all levels of intensity / causality might be higher than the overall number of subjects with at least one AE.

Incidence of all reported AEs, TEAEs, SAEs and non-serious AES (classified by primary System Organ Class (SOC) and Preferred Term (PT)) will be tabulated by treatment group. In addition, summary tables will be presented by maximum intensity, drug relationship and TEAEs/SAEs associated with premature withdrawal of study.

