Note: In the event of multiple occurrence of a same AE (same Preferred Term) by the same subject, the maximum intensity (severe > missing > moderate > mild) and the most serious causality (related > not related) will be chosen.

SAP Final Version: 15 July 2019

27/50

Note: In case of missing data for relationship/intensity, the AE (PT) will be presented with the most severe category (related and/or severe) when crossing intensity and relationship.

3.2.2.2 *Laboratory data*

Not applicable.

3.2.2.3 *Vital signs*

Vital signs will be listed at each assessment by treatment group and subject. Any unscheduled vital signs will be flagged [U] in the listing.

Baseline values (values at first visit) will be defined as the last vital signs measurement collected prior to the first dose of study drug.

Summary statistics by treatment group will be presented (blood pressure, heart rate in sitting position, body temperature and body weight) at each scheduled assessment for actual values and changes from baseline.

3.2.2.4 *ECG*

Not applicable.

3.2.2.5 *Other assessments (as applicable)*

Any new or worsening clinically significant abnormal physical examination results should be recorded on the Adverse Event eCRF page and will be part of the AE analysis.

3.2.3 *Missing data and outliers*

3.2.3.1 *Missing data*

If there is a significant number of missing values for a subject (or if there is confirmed data appearing spurious), a decision will be made following consultation with the sponsor regarding the handling of these data in summaries, prior to breaking the blind.

Any repeat or additional assessments performed will be included in the individual subject data listings.

3.2.3.2 *Missing or incomplete dates*

Missing date and/or time related to stools in patients diaries for time-to-event analyses (time to recovery, time to first formed stool, time to last watery stool, time to recovery without confirmation):

Rules of imputation for events: in case of time information is missing but information on date and on stool consistency are available, the time will be imputed:

- to 23:59 if there is no other subsequent stools the same day,
- to time of the next stool the same day minus 1 minute otherwise.

Rules of imputation for censoring: in case of time information is missing but information on date and on stool consistency are available, the time will be imputed:

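### Adverse-event observation time depends on recovery, the primary outcome, so crude AE percentages tilt slightly towards diosmectite if it works, and Visit 3 vital signs are not a randomised comparison.

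*SAP*

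**What the plan says.** Tolerability against placebo is a secondary objective: "To assess the clinical tolerance of diosmectite versus placebo" (SAP 1.1.2).

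**Length of treatment and follow-up.** Protocol 6.1 makes 24 sachets mandatory; after that, treatment ends at recovery or at 48 sachets. Protocol 5.2.2 adds: "A last visit (Visit 3) will be planned at Day 9 or 10 for subjects who did not recover by Visit 2". SAP 1.2.2 gives participation as 5-6 days for subjects recovered by Visit 2 and 9-10 days otherwise.

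**AE windows.** Protocol 3.2.3 and 8.1 and SAP 1.3.2.2, 3.1.3 and 3.2.2.1 all monitor AEs from consent to 7 days after treatment ends. The SAP counts TEAEs "from the first study drug intake until 48h after last study drug intake". The visit-level text differs. The 7-day extension appears at Visit 3 (Protocol 5.2.3 and Table 2, footnote d) and at early withdrawal (5.2.4), but Visit 2 (5.2.2) mentions only events since the previous visit. Protocol 8.1.1 ends the AE definition at end of study, which Section 3.5 ties to recovery and the last follow-up visit. No contact after Visit 2 is scheduled for recovered subjects.

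**Summaries.** SAP 3.2.2.1 presents "Incidence of all reported AEs, TEAEs, SAEs and non-serious AES" by arm as numbers and percentages of subjects. Study exposure (SAP 3.2.4) and drug exposure (SAP 3.2.8) are summarised separately and enter no AE table. SAP 3.2.2.3 summarises vital signs by arm "at each scheduled assessment for actual values and changes from baseline", which includes Visit 3.

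**The concern.** The rules are identical in both arms, but how long a subject is observed is decided by the outcome the drug is meant to change. If diosmectite works, more placebo subjects are still unrecovered at Visit 2, take more sachets and are observed longer. With equal daily AE rates, the crude table would then show somewhat fewer AEs on diosmectite, and the same shortfall could hide part of a real excess.

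For vital signs the issue is selection, not time. The Visit 3 columns contain only subjects chosen after randomisation by failure to recover, in different proportions by arm.

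**Working it through.** **Inputs.** SAP 1.3.4: "Assuming a median time to recovery of 55 hours in the active group and 70 hours in the placebo group". Protocol 10.2: "a significance level of 5% and a power of 80" per cent, with losses of "a maximum of 5% subjects prematurely withdrawn without recovery and a maximum of 10% nonevaluable subjects". Visit 2 on Day 5/6 is taken as 96-120 h after first intake, and Visit 3 as 96 h later. Assumptions: no withdrawals; an AE hazard that is constant over time and equal in both arms.

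**Plan's own figure.** With exponential times, P = 70/(55+70) = 0.56. N = (1.960+0.842)²/[12×0.25×(0.56−0.50)²] = 7.849/0.0108 = 726.7, against 726 stated. 726/(1−0.15) = 854.1, against 854 stated. Exponential recovery at these medians is therefore consistent with the plan.

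**Unrecovered at Visit 2.** S(t) = 0.5^(t/m), with m = 55 or 70 h.
- 96 h: 29.8% diosmectite, 38.7% placebo (127 and 165 of 427).
- 120 h: 22.0% and 30.5% (94 and 130 of 427).

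**Mean time to last intake.** D = V2 + (m/ln 2)×[S(V2) − S(V2+96 h)].
- V2 = 96 h: 4 + 0.69 = 4.69 days; 4 + 1.00 = 5.00 days.
- V2 = 120 h: 5 + 0.51 = 5.51 days; 5 + 0.79 = 5.79 days.

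**Mean observed time in days, diosmectite/placebo.**

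| Reading | Formula | V2 = 96 h | V2 = 120 h |
|---|---|---|---|
| AE, 7 days for all | D + 7 | 11.69/12.00 = 0.974 | 12.51/12.79 = 0.978 |
| TEAE, 48 h for all | D + 2 | 6.69/7.00 = 0.956 | 7.51/7.79 = 0.965 |
| Collection ends at last visit | V2 + 4×S(V2) | 5.19/5.55 = 0.936 | 5.88/6.22 = 0.946 |
| Visit-level text taken literally | D + 7×S(V2) | 6.78/7.70 = 0.880 | 7.05/7.92 = 0.891 |

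The last row observes recovered subjects to Visit 2 and unrecovered subjects to 7 days after last intake. The TEAE ratio is 0.950-0.956 if last intake is instead put 12 h before each subject's last visit.

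**Effect on crude percentages.** The documents give no AE rate, so 10% on diosmectite is assumed. Placebo then shows 1 − 0.9^(placebo time/diosmectite time):
- 7-day AEs: 10.25% or 10.21%, an excess of 0.2-0.25 points.
- TEAEs: 10.43% or 10.35%, an excess of 0.35-0.43 points.
- Literal visit-level text: 11.28% or 11.12%, an excess of 1.1-1.3 points.

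For diosmectite incidences of 5-30% the excess is 0.1-0.65 points (7-day) and 0.2-1.1 points (TEAE).

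**Sensitivity.** With S(t) = 0.5^((t/m)^k) and k from 0.8 to 1.5, placebo time is longer by 1.8-2.8% (7-day) and 3.1-4.9% (TEAE). The literal reading runs from 7.68/8.42 = 0.91 (k = 0.8, 120 h) to 5.70/6.89 = 0.83 (k = 1.5, 96 h).

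**Against sampling error.** The standard error of a 10% versus 10% difference is √(2×0.10×0.90/427) = 2.1 points.

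**The case against.** A reader might infer that AE observation simply ends at Visit 2 for recovered subjects and at Visit 3 for the rest. The general AE rules in both documents do not support that. A recovered subject who stops on Day 4/5 stays in the AE window to about Day 11/12, and the TEAE window runs to about Day 6/7. The ratios of 0.94-0.95 and 0.88-0.89 arise only if collection after Visit 2 lapses in practice for recovered subjects, which the visit-level text allows but does not establish.

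A reader might also suppose that unrecovered subjects have a higher AE rate, which would enlarge the effect. The documents give no such rate, and Protocol 8.1.1 generally keeps symptoms of the baseline diarrhoea out of AE reporting.

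It can further be argued that incidence per treatment course is a legitimate measure, since a shorter course with fewer events is a consequence of treatment. Only the primary analysis is confirmatory (SAP 3.1.4), no AE test is described, exposure is tabulated, and the documents are open that Visit 3 is for unrecovered subjects. All of this stands. It makes the crude tables acceptable as description and the bias small: 0.2-0.4 points is about 0.1-0.2 of a standard error. It does not make the windows equal, supply an AE comparison over a common window, or turn the Visit 3 columns into a randomised comparison.

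**Conclusion.** The point holds as a minor one. Observation for AEs and TEAEs depends on the primary outcome, and no planned AE table allows for it. Under the windows stated for all subjects the ratio of observed time is 0.97-0.98 for AEs and 0.95-0.96 for TEAEs, a tilt of roughly 0.2-0.4 points at 10% incidence, in favour of diosmectite if it works. Under the literal visit-level text the ratio is 0.88-0.89 and the tilt about 1 point. The documents do not settle which applies, and that contradiction is the part most worth resolving.

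These sizes rest on the plan's medians, exponential recovery, no withdrawals and a constant, equal AE rate. If diosmectite has no effect on recovery, the tilt vanishes. The vital-signs point needs no AE-rate assumption: Visit 3 would compare about 94-127 diosmectite with 130-165 placebo subjects, before withdrawals. The direction of any bias there cannot be derived from the documents.

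**What to change.** 1. **SAP 3.2.2.1.** Add AE and TEAE incidence by arm (overall, by SOC/PT, and related TEAEs) for events with onset from first intake to Visit 2 or early withdrawal, and name it as the between-arm tolerability comparison. This window is planned for every subject and is valid under either reading of the AE rule. Keep the whole-study tables as descriptive.
2. **Any rate per subject-days** must use one window in numerator and denominator; for TEAEs, first intake to last intake plus 48 h. A first-intake-to-last-visit denominator under 7-day event counts would show a true ratio of 1.00 as (11.69/5.19)/(12.00/5.55) = 1.04 or (12.51/5.88)/(12.79/6.22) = 1.03.
3. **Reconcile the AE window** across Protocol Table 2 (footnote d), 5.2.2-5.2.4, 8.1 and 8.1.1 and SAP 3.2.2.1. The SAP is dated July 2019 and the study period is planned to September 2019, so the SAP should at least state what was collected after Visit 2 for recovered subjects.
4. **SAP 3.2.2.3.** Label Visit 3 vital signs as the subset unrecovered at Visit 2, not for comparison between arms. Visit 2 serves as the all-subject comparison. A last-visit row is optional, since it mixes Day 5/6 with Day 9/10.

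Cost: SAP wording and a few tables from data already collected, plus clarification of the protocol text. The common-window table leaves out later events, which remain in the crude tables.

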3.2.6.2 Other Baseline characteristics

- History of disease: diarrhoea episode characteristics will be summarized using the following information from the “History of current acute diarrhoea episode” eCRF page:
 - Duration since diarrhoea diagnosis (hours): summary statistics
 - Time since diarrhoea onset: number (%) in categories [0-12H]; [12-24H]; [24-36H]; [36-48H]; ≥48H.
 - Number of stools during the last 24 hours: summary statistics on overall and for:
 - Stools/unformed loose or watery stools of the first 12 hours-period
 - Stools/ unformed loose or watery stools of the second 12 hours-period
 - Presence of associated symptoms during the last 24 hours: number (%) of subjects in each category Nausea (Yes/No), Vomiting (Yes/No), Abdominal pain (Yes/No), Anal irritation (Yes/No).
- Results of virology/microbiology for stool examination:
 - Results of Virology testing with number (%) of subjects in each category: Rotavirus, Adenovirus, Norovirus, None, Missing.
 - Results of Bacteriology and parasitology testing with number (%) of subjects in each category:
 - Bacteriology subgroups: Enteropathogenic and enterotoxigenic E. Coli, Staphylococcus aureus, Shigella, Salmonella, Campylobacter, Yersinia enterocolitica, None, Missing.
 - Parasitology subgroups: Aemibiasis (entamoeba histolytica), Giardia/lamblia, None, Missing.
 - Additionally, above frequency tables will be provided with number (%) of patients with a positive result to:
 - Virology and parasitology,
 - Virology and bacteriology,
 - Parasitology and bacteriology,
 - Virology, bacteriology and parasitology.

3.2.7 *Medical and surgical history, Non-Drug therapies, concomitant surgical procedures*

Medical and surgical history will be coded using MedDRA Version 22.0 as well as Prior and Concomitant Non-Drug therapies and Concomitant Surgical Procedures.

Listings will present the preferred term and verbatim text. The listings will be sorted by treatment group, subject, primary system organ class, preferred term and verbatim text.

Frequency tables of the number and percentage of subjects will be provided by primary system organ class and preferred term for each treatment group for:

SAP Final Version: 15 July 2019

31/50

- Prior medical and surgical history: separately for prior and ongoing conditions
- Concomitant non-drug therapy
- Concomitant surgery.

Prior non-drug therapies will only be listed.

In the event of multiple incidences of the same primary system organ class /preferred term being reported by the same subject, the subject will be counted once for that primary system organ class/preferred term.

These summaries will be produced on the safety population.

3.2.8 *Subject compliance*

Data collected from both “Study Treatment Administration (on site)” eCRF section and “Study drug intake” part of the DEB will be presented in individual listings with information such as date of intake, time of intake when taken on site and number of sachets taken by the subject. Listings will be ordered by treatment group, subject and visit, for all subjects of the Safety set.

Study drug exposure (days) will be summarized on the safety population.

Summary statistics on number of sachets taken during the mandatory period (from Day1 to Day4/Day5), until recovery and until end of study will be displayed by treatment group.

Compliance will be expressed in percentage as the total sachets taken based on the expected total sachets to be taken and will be calculated during the mandatory treatment period for all subjects, until the recovery for subjects with recovery and until the end of study for subjects with no recovery (see section 3.2.12). Compliance will be categorized as < 80% (Under compliance), 80-120% (Compliance) and > 120% (Over compliance) and will be summarized in percentage and in class overall, on the safety population.

3.2.9 *Prior and concomitant therapies*

Two types of medications will be analysed:

- **General medications:** using the information retrieved from the “Prior and Concomitant Medications (Excluding current acute diarrhoea episode)” eCRF section.
- **Medications related to current diarrhoea episode:** using the information retrieved from the “Prior and Concomitant Medications for the current acute diarrhoea episode” eCRF page.

Prior medications are defined as the medications taken within 30 days preceding visit 1 and stopped prior to the first study drug intake.

Concomitant medications are defined as medications that have been taken during the treatment period regardless the start or stop date. For any partial date, if it is not clear when the medication started or ended but shows a possibility that it has been taken during the treatment period then it will be considered as a concomitant medication.

All therapies will be coded using the latest version of WHO-Drug Dictionary. The therapeutic class will correspond to the second level of ATC code, that is, corresponding to the first 3 figures (see section 3.2.12-Derived data).

Listings will be presented for the therapeutic class, preferred term and verbatim text. The listings will be sorted by treatment group, subject, chronological start date, therapeutic class, preferred name and verbatim name.

Frequency tables of the number and percentage of subjects in the safety population for each treatment group and on overall, by therapeutic class and preferred name will be provided:

- for general prior and concomitant therapies,
- for prior and concomitant therapies for acute diarrhoea.

3.2.10 *Pharmacokinetics & antibodies (if applicable)*

Not applicable.

3.2.11 *Pharmacodynamics (if applicable)*

Not applicable.

3.2.12 *Derived data*

The derived data are variables which are calculated from the raw data in the eCRF or DEB data and not included in the database.

Efficacy derived variables:

Primary endpoint:

- Time to recovery = Time (hours, minutes) from the 1st study treatment intake to the first formed stool (this formed stool must have been followed by a nonwatery stool):
(Date/time of Recovery or last date/time of stool (if censored) – date/time of 1st treatment intake).

The subject will be considered to have recovered if the subject records a stool with a formed consistency corresponding to Type 1 to Type 4 (inclusive), followed by a nonwatery stool corresponding to Type 1 to 5 (inclusive). Dates and times will be retrieved from the DEB filled in by the subject. Imputations rules in case of partial time variables are described in section 3.2.3.2. Stools without consistency evaluation will not be taken into account for the determination of recovery.

Rules of censoring are described in the table below:

Event	Decision	Date of event or censoring to consider for the analysis
Recovery	Not censored	Date/time of first form stool followed by a nonwatery stool
No recovery and subject completed the study	Censored	Date/time of last stool
No recovery and subject prematurely withdrawn the study	Censored	Date/time of last stool

Event	Decision	Date of event or censoring to consider for the analysis
No recovery and no post-baseline evaluation of stools	Censored	Date/time of first IMP intake (if administered)
		Date/time of randomisation (if not administered)

Secondary endpoints:

- Time from diarrhoea onset to recovery (hours) will be calculated as follows:

(Date/time of Recovery or last date/time of stool (if censored) – date/time of diarrhoea onset).

The date and time of diarrhoea onset will be the start date/time of first unformed loose or watery stool as recorded in the “History of current acute diarrhoea episode” eCRF page.

Rules of censoring are the same as described for primary endpoint.

- Time from diarrhoea onset to the first formed stool (hours) will be calculated as follows:

(Date/time of 1st formed stool or last date/time of stool (if no formed stool) – date/time of diarrhoea onset).

The date of 1st formed stool will be the earliest date of stools with a formed consistency corresponding to type 1 to 4, whatever the consistencies of the next stools.

Rules of censoring are described in the table below:

Event	Decision	Date of event or censoring to consider for the analysis
Formed stool	Not censored	Earliest Date/time of formed stool
No formed stool and subject completed the study	Censored	Date/time of last stool
No formed stool and subject prematurely withdrawn the study	Censored	Date/time of last stool
No formed stool and no post-baseline evaluation of stools	Censored	Date/time of first IMP intake (if administered)
		Date/time of randomisation (if not administered)

- Time from the first study treatment intake to the last watery stool (hours) will be calculated as follows:

(Date/time of last watery stool or last date/time of stool (if censored) – date/time of 1st treatment intake).

The date of last watery stool will be the latest date of stools recorded by the subject, with a consistency corresponding to type 6 or 7.

Rules of censoring are described in the table below:

Event	Decision	Date of event or censoring to consider for the analysis
Watery stool	Not censored	Date/time of last watery stool

SAP Final Version: 15 July 2019

34/50

Event	Decision	Date of event or censoring to consider for the analysis
No watery stool and subject completed the study	Censored	Date/time of last stool
No watery stool and subject prematurely withdrawn the study	Censored	Date/time of last stool
No watery stool and no post-baseline evaluation of stools	Censored	Date/time of first IMP intake (if administered)
		Date/time of randomisation (if not administered)

- 12-hour period (for analysis of number of stools and number of watery stools): is defined as the number of hours between the date/time of stool recorded in the DEB and the date/time of first IMP intake and will be expressed in time intervals of 12 hours ([0-12h], [12-24h], [24-36h]....).

Other derived variables

The following derived data will be calculated and included in the listings:

- **Study day**

Study day based on the 1st treatment intake will be calculated as following:

If the date was on or after treatment intake then

$$\text{Study day} = \text{Date} - \text{date of study treatment intake} + 1$$

If the date was before treatment intake then

$$\text{Study day} = \text{Date} - \text{date of study treatment intake}.$$

- **Study exposure (days)**

Study exposure (days) will be calculated as follows:

$$\text{Exposure (days)} = (\text{Date of Last Study Visit} - \text{Date of Informed Consent} + 1).$$

- **Study Drug Exposure (days)**

$$\text{Drug exposure (days)} = (\text{last sachet intake date} - \text{first sachet intake date} + 1).$$

- **Compliance (%)**

Compliance of study medication will be calculated as follows:

$$\text{Compliance (\%)} = (\text{Total sachets taken} / \text{Expected total sachets}) \times 100.$$

(a) During the mandatory treatment period:

Expected total sachets = 24 therefore,

$$\text{Compliance} = (\text{Total sachets taken from Day1 to Day4 or Day5}) / 24.$$

The number of sachets taken by the patient during the mandatory period will be derived according to the time of day at which the subjects has taken the first of two sachets on day 1: in the morning if the first two sachets have been taken before 11:00 a.m. (<11:00 a.m.), the afternoon if taken between 11:00 a.m. and 6:00 p.m. ([11:00 a.m.; 6:00 p.m.]) and the evening if taken after 6:00 p.m. (>6:00 p.m). Patients with a missing time of first administration will be considered to have taken their first two sachets in the morning (i.e. before 11:00 a.m.).

(b) Until recovery for subjects with recovery:

Expected total sachets will be calculated using date and time of recovery according to diary:

Expected total sachets = (Date of confirmation of Recovery – Date of 1st sachet intake +1) * 6⁽¹⁾ ⁽²⁾.

⁽¹⁾: the expected number of sachets for each day is theoretically 6 sachets. For the day of recovery, according to the time of last nonwatery stool which immediately follows the recovery (confirmation of recovery), the theoretical number of sachets will be: 0 sachet if time of the last nonwatery stool is before 07:00 a.m. (<7:00 a.m) (i.e. the subject is considered to have taken no sachet the day of recovery), 2 sachets if time of last nonwatery stool is between 7:00 a.m. and 12:00 p.m. ([7:00 a.m.;12:00 p.m.]), 4 sachets if time of last nonwatery stool is between 12:00 p.m. and 7:00 p.m. ([12:00 p.m.;7:00 p.m.]) and 6 sachets if time is over 7:00 p.m. (>7:00 p.m).

In case of missing data, the time of confirmation of recovery will be imputed as follows:

- if the day of confirmation is the same as the day of recovery, time of confirmation will be imputed by the time of recovery +1 minute
- if the day of confirmation is not the same, date and time of confirmation will be imputed by the day of confirmation and time to 00:01 a.m.

⁽²⁾: the number of expected sachets to be taken on the first day of intake will depend on the time of the first intake. If the first sachets were taken after noon by the subject, 2 sachets will be subtracted from the total expected number of sachets for that subject at day 1.

If the recovery occurs the day corresponding to the first IMP intake, the total expected sachets will be the minimum between the theoretical number of sachets estimated using the time of recovery as described in (1) and using the time of the first IMP as described in (2).

The number of sachets taken by the subject the day of the recovery will be calculated using the time of the confirmation of the recovery only if the number of sachets taken that day is more or equal 6: the subject is considered to have taken 0 sachet if this time is before 7:00 a.m. (<7:00 a.m), 2 sachets if this time is between 7:00 a.m. and 12:00 p.m. ([7:00 a.m.;12:00 p.m.]) and 4 sachets if this time is between 12:00 p.m. and 7:00 p.m. ([12:00 p.m.;7:00 p.m.]). If subject took less than 6 sachets the day of the recovery, the number of sachets taken by the subject is equal to the number of sachets as declared in the diary.

- (c) Until the end of study for subjects without recovery:

For the calculation of the compliance, the expected total sachets will be based according to the last visit date of the subject:

For the first day, the number of expected total sachets taken will depend on the time of day at which the subject has taken the first two sachets (cf. rules described in paragraph a). For the subsequent days, the theoretical number of sachets will be 6 by diary day until the last day of the diary, plus:

- 2 sachets if the subject declared to have taken any sachet the last day in the diary (or information is missing in the diary)

- the number of sachets taken by the subject that day if the subject took at least one sachet the last day.

In case of premature withdrawal, if date of collection or date of withdrawal is completed, then the expected total sachets to be taken by the subject will be based on the last available date in the diary.

If patient ended the study on the day of first administration then the expected total sachets will be the minimum between expected sachets according to the time of first administration as described in (a) and the number of sachets taken by the patient that day.

The number of sachets recorded in the DEB on Day 1 (“Study Drug intake” section) includes the first 2 sachets taken on site.

Compliances for patients without diary or with no information on their diary regarding the number of sachets will not be calculated.

- **Change from baseline**

Change from baseline at a given visit will be calculated as a difference from baseline (assessment at the first visit).

- **Therapeutic Class**

The therapeutic class will correspond to the first 3 figures of the ATC code. The decoding of the therapeutic class will be done from the latest version of WHO-Drug Dictionary.

- **Age**

Age (years) will be calculated as follows and truncated to the largest integer that is less than or equal to the calculated result:

$$\text{Age} = (\text{date of first Visit} - \text{birth date} + 1) / 365.25.$$

- **BMI**

BMI (kg/m^2) at Baseline will be derived as $\text{Weight (kg)} / [\text{Height(cm)} / 100]^2$ measured at first visit and rounded to the nearest decimal.

- **Season of randomisation**

Season of randomisation will be derived from the month of the randomisation date as follows:

- Summer: if month (randomisation date) is from April to October inclusive,
- Winter: if month (randomisation date) is from November to March inclusive).

- **Duration since diagnosis of current acute diarrhoea**

Duration since current diarrhoea diagnosis (in hours) will be defined using the date/time of diarrhoea onset as recorded in the “History of current acute diarrhoea episode” eCRF page:

$$\text{Duration (hours)} = (\text{date/time of randomisation} - \text{date/time of diarrhoea onset}).$$

- **AE duration**

If the start and end dates of the AE are identical then “<1” day will be presented. If the duration is greater than 24 hours then it will be calculated as (end date - start date) +1 and presented in days. If the recorded end date is CONT. (for continuing), the end date will be listed as “ongoing” and the duration will be approximated as “ \geq (last attended visit date - start date)+1” day(s). If the start date or the end date are

partial the duration will be presented as a superior inequality “≥xx” day(s) (i.e., ≥2 where start date = 31 January 2004 and end date = February 2004 or start date = January 2004 and end date = 01 February 2004].

- **Time since last treatment intake for adverse event**

If the start date of the adverse event is identical to the date of last administration intake, then “<1” day will be presented. If the time to onset is greater than 24 hours then it will be calculated as (start date – last treatment intake date) +1 and presented in days.

If the start date is partial, the time since 1st treatment intake will be presented as a superior inequality (i.e., for an AE started in February 2004 after the last treatment intake performed on 31 January 2004, the time since last treatment intake will be as “≥2” days). If the start date is missing the time since last treatment intake will not be presented.

- **Concomitant therapy duration:**

The duration of concomitant treatments will be calculated as (end date – start date) + 1. If the recorded end date is CONT. (for continuing), the end date will be listed as “ongoing” and the duration will be approximated as “≥ (last attended visit date – start date)+1” day(s). If the start date or the end date are partial, the duration will be presented as an inequality “≥ xx” day(s) (i.e. ≥2 where start date=31JAN2004 and end date=FEB2004 or start date=JAN2004 and end date=01FEB2004) but if both are partial or one is missing, the duration will not be presented.

- **Medical and surgical history duration**

The duration of medical and surgical history will be calculated as (end date – start date) + 1. If the recorded end date is CONT. (for continuing), the end date will be listed as “ongoing” and the duration will be approximated as “≥ (visit 1 day 1 date – start date)+1” day(s). If the start date or the end date are partial, the duration will be presented as an inequality “≥ xx” day(s) (i.e. ≥2 where start date=31JAN2004 and end date=FEB2004 or start date=JAN2004 and end date=01FEB2004) but if both are partial or one is missing the duration will not be presented.

3.2.13 *Visit windows (optional)*

All data will be organised and analysed according to the scheduled visits outlined in the protocol. As defined by the protocol, visit 1 (baseline visit) has to be performed within 48 hours after onset of diarrhoea. Visit 2 will correspond to Day 5 or Day 6 and Visit 3 (if any) will correspond to Day 9 or Day10.

3.2.14 *Rules and data formats*

Data will be presented using an appropriate number of decimal places (i.e. the number of decimal places used does not imply undue precision). Raw data will be presented to the number of decimal places collected, and derived data will be presented to an appropriate number of decimal places. The appropriate number of decimal places will be determined by general practice, mathematical rationale or scientific rationale (e.g. age should be presented in whole numbers).

For summary statistics, the following will be presented n, number of missing values, arithmetic mean, standard deviation, median and the range (minimum, maximum).

Mean, median, standard deviation and standard errors of the mean (SE) values will be reported to one decimal place greater than the raw/derived data that they summarise. Minimum and maximum values will be reported with the same precision as the raw data.

Percentages will be reported to one decimal place and 0% will not be presented. Percentages will be calculated using a denominator of all subjects in a specified population. Missing values will not be accounted for in denominator. The denominator will be specified in a footnote to the tables for clarification if necessary.

Lower and upper confidence interval values should be presented to one decimal place more than the raw/derived data (i.e., to the same number of decimal places as the mean).

Percentiles (e.g., 25%, 75%) should be presented to one decimal place more than the raw/derived data.

Time-to-event endpoints will be descriptively summarized using Kaplan-Meier (KM) product-limit estimators.

P-values will be reported to four decimal places (e.g.: $p=0.0037$), after rounding. P-values which are less than 0.0001 will be presented as '<0.0001'.

All text fields must be left justified and numeric or numeric with some text specification (e.g.: not done, unknown, <4.5, ...) must be decimal justified. Dates will be presented in the format [yyyy-mm-dd] and times in the format [hh:mm].

